#### 4.1.6.1 Pulmonary Gas Exchange Measures

Breath-by-breath pulmonary gas exchange data will be smoothed using a middle five of seven breath average. Key variables of interest include: the first ventilatory threshold (VT1), the respiratory compensation point (RCP), peak oxygen consumption ( $\dot{V}O_{2\text{peak}}$ ) and end-tidal CO2.  $\dot{V}O_{2\text{peak}}$  is defined as the mean  $\dot{V}O_2$  over the last 30 seconds of the exercise test, adjusted for body mass (ml·kg·min). VT1 will be determined by using the V-slope method to identify the deflection point in the relationship between  $\dot{V}CO_2$  and  $\dot{V}O_2$  – indicating a disproportionate rise in CO2 production due to increasing anaerobic glycolytic activity (65). VT1 will be confirmed using the nadir of the ventilatory equivalent (VE) for  $\dot{V}O_2$  (VE/ $\dot{V}O_2$ ) (65). The RCP will be determined using the V-slope method to identify the deflection point in the relationship between VE and  $\dot{V}CO_2$  – which marks the onset of hyperventilation caused by excessive blood lactate accumulation (65). The RCP will be confirmed using the nadir of VE/ $\dot{V}CO_2$  (65). The VT1 and the RCP will be confirmed by two researchers at each site. Where agreement is not reached, a third researcher will adjudicate. End-tidal CO2 is the partial pressure of CO2 measured at the end of each breath.

Exercise termination criteria
Chest pain suggestive of ischaemia
Fall in systolic blood pressure $>20$ mmHg from the highest value during exercise
$>225$ mmHg systolic blood pressure
$>130$ mmHg diastolic blood pressure
Hypotension ( $<100$ mmHg systolic)

Severe desaturation: $\text{SpO}_2 \leq 80\%$ when accompanied by symptoms of severe hypoxaemia
Sudden pallor
Loss of coordination
Mental confusion
Dizziness or faintness
Signs of respiratory failure

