Description of interventions	Consecutive day 2 day CPET and follow up for 7 days for subjective feelings/fatigue.
Duration of study	
Study Duration:
 
 
- Total trial duration 12 months 
 
○ Recruitment 6 months (November 2022 to April 2023)
 
○ Data Collection (November 2022-April 2023)
 
○ Analysis and reporting: 4 months (April 2023-July 2023)
 
 
 
- Participant Duration: 3 sessions (1 Familiarisation, 2 CPET on consecutive days) and 1 week follow up
 

Randomisation and blinding	None

Study Investigators	
Chief Investigator: [name] Senior Lecturer in Exercise Physiology School of Human Sciences University of Derby, UK	Principle Investigator (Sheffield, UK) [name] Senior Research Fellow Advanced Wellbeing Research Centre Sheffield Hallam University, UK
Principle Investigator (Chicago, USA) [name] Clinical Associate [name] of Physical Therapy University of Illinois at Chicago Chicago, USA	Principle Investigator (Bengaluru, India) [name] [name] Assistant Professor, Department of Physiotherapy Ramaiah Medical College, Bengaluru, India
Co-Investigator: [name] [name] of Physical Therapy University of Illinois at Chicago Chicago, USA	Co-Investigator: [name] Lecturer in Exercise Physiology School of Human Sciences University of Derby, UK
Co-Investigator: [name] Director, Advanced Wellbeing Research Centre Sheffield Hallam University	Co-Investigator: [name] Consultant Respiratory Physician University Hospitals of Derby and Burton Derby, UK
Co-Investigator: [name] Assistant [name] of Physical Therapy University of Illinois at Chicago Chicago, USA	Co-Investigator: [name] School of Human Sciences University of Derby
Co-Investigator: [name] Researcher, Advanced Wellbeing Research Centre, Sheffield Hallam University.	Co-Investigator: [name], Principal Research Fellow, Advanced Wellbeing Research Centre, Sheffield Hallam University.
Co-Investigator: [name], Associate Professor, Advanced Wellbeing Research Centre, Sheffield Hallam University.	Co-Investigator:

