## **4.0 Study Protocol**

Each test will be interpreted following published guidelines provided by the American College of Sports Medicine. Upon the conclusion of each test, the key descriptive characteristics and findings will be recorded to facilitate the use of cohort analyses. Data will be stratified according to the demographic (age, gender, ethnicity, pre-COVID-19 functional status and important physiological parameters for a given workload (absolute and relative oxygen consumption or  $VO_2$  peak,  $O_2$  pulse, alveolar-arterial  $O_2$  gradient, arterial to end-tidal  $CO_2$  difference and the relationship between carbon dioxide output and ventilation ( $V_E/VCO_2$  slope))). These approaches will be used to identify differences, trends and patterns in key defining variables that might lead to longstanding impairment/morbidity. Study day 1 will be conducted 7-10 days post baseline measures to ensure no symptoms of post exertional malaise and/or excessive fatigue from baseline assessments. Patients will wear accelerometers during this period to compare baseline and follow up.

Baseline	Session 2	Session 3 (+1 day)	7 Day follow up
Anthropometrics Questionnaires Symptom Profile* Lung Function TUG 6MWT	Symptom Profile* ECG Resting HR + BP CPET Lactate and BP Recovery following CPET HRV	Symptom Profile* ECG Resting HR + BP CPET Lactate and BP Recovery following CPET HRV	Accelerometry Patient Log/Diary HRV

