A step-wise incremental exercise test will be performed at a cadence of 60 revolutions per minute (rpm) ( $\pm 10\%$ ). The exercise protocol will begin with a 3-minute rest period, followed by a step-wise incremental protocol, designed to achieve volitional exhaustion within 8-12 minutes of exercise onset. The exercise protocol will be individualised based on participants' predicted exercise capacity, as described above. Heart rate and pulmonary gas exchange data will be measured continuously. Blood pressure and rating of perceived exertion (RPE) (6 to 20 scale) will be measured during the final 15 second period of each minute. For blood pressure measurements, participants will be asked to relax their arm and shoulder muscles whilst their forearm is rested on the researcher's shoulder (padded with a folded towel). This will ensure that the participant's arm is positioned near heart level to reduce measurement error. At the end of the exercise test, participants will complete a cooldown consisting of unloaded pedalling at 20rpm for 5-10 minutes. All data will be exported for offline analysis using Microsoft Excel (Washington, USA).

Criteria for the assessment of a good participant effort will include peak respiratory exchange ratio (RER)  $>1.10$ , peak HR $\geq 85\%$  predicted and RPE  $\geq 18.31$  (Balady et al., 2010). Prior to the test, participants will be monitored for 5 minutes to allow passive data collection and for a total of 10 minutes after completion.

We will analyse over 30s averages to allow for differences in Gas analysis systems and monitor heart rate throughout test and 10 minutes seated recovery. Blood Pressure monitoring continuously (every 30s). Blood lactate concentration will be monitored through fingertip sampling at the end of each stage and at 5-minute intervals for 30 minutes following volitional fatigue.

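### VT1 and RCP are settled by site readers with no masking to test day, so any day-1 versus day-2 threshold comparison is open to reader expectation of unknown size

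*Protocol*

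**What the plan says.** Section 4.1.6.1 introduces the thresholds first in its list: "Key variables of interest include: the first ventilatory threshold", followed by RCP, peak oxygen consumption and end-tidal CO2. On method, "VT 1 will be determined by using the V-slope method to identify the deflection point" in the VCO2–VO2 relationship, and the nadir of VE/VO2 serves as a check. RCP is handled in the same way, from VE against VCO2, with the nadir of VE/VCO2 as the check. The two thresholds "will be confirmed by two researchers at each site". "Where agreement is not reached, a third researcher will adjudicate".

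The synopsis describes the design as "Consecutive day 2 day CPET and follow up for 7 days for subjective feelings/fatigue". Its row headed "Randomisation and blinding" reads None. Section 4.0 adds: "Upon the conclusion of each test, the key descriptive characteristics and findings will be recorded to facilitate the use of cohort analyses". Section 4.1.6 states: "All data will be exported for offline analysis using Microsoft Excel".

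The protocol does not say that the two readings are independent. It does not say that the readers or the adjudicator are masked to test day, symptoms or the other day's result.

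**The concern.** A V-slope breakpoint leaves room for judgement, and the adjudication rule accepts that two readers can differ. If readers expect a worse response on the second day, they may place a doubtful breakpoint a little earlier on that day. The shift then falls on the within-person day difference.

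The existing arrangements deal with other kinds of error. A second reader and an adjudicator reduce random error, but not an expectation that all three share. Stable differences between sites' readers largely cancel within a participant if the same people read both days, whereas a day-related expectation does not cancel. Recruiting more participants narrows the interval around a shifted mean, so the shift looks more convincing.

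At stake is whether a reported fall in VT1 or RCP from day 1 to day 2 can be credited to physiology. Analysis alone cannot repair this once unmasked readings have been recorded.

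**Working it through.** The protocol gives no figure to reproduce. Section 3.2 and the synopsis state 150 participants (50 per centre) with no alpha, power, effect size or SD. The check is therefore a comparison of the relevant sections, followed by an illustration of how sensitive a paired comparison is.

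**1. Are readers masked?** Three statements bear on this:
- Section 4.1.6.1 places the two readers at the participant's site and says nothing about masking or independence.
- The synopsis gives blinding as None.
- Section 4.0 has findings recorded at the end of each test, when the day would normally be known. Its schedule also places a symptom profile at both CPET sessions.

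Together these provide no masking and make knowledge of the day likely. They do not state that readers know it.

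**2. Is a day comparison planned?** The synopsis fixes CPET on two consecutive days, Section 2.2 lists the prevalence of post-exertional malaise as a secondary aim, and Section 4.5 plans tests of within-group differences. None of these names a day-1 versus day-2 contrast in VT1 or RCP. The contrast is implied by repeating the test the next day.

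**3. Does anything in test conduct need the thresholds at once?** The starting load in Section 4.1.6 depends on six-minute walk distance. None of the termination criteria listed in Section 4.1.6.1 uses VT1 or RCP. Delayed reading therefore interferes with neither.

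**4. Illustration.** Assumed, and not in the protocol: a paired mean comparison, normal approximation, two-sided alpha 0.05, 80% power, no true day effect, and a systematic reading shift b expressed in SDs of the paired difference. The values of n are the protocol's 150 in total and 50 per centre.

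- Smallest detectable difference = (1.96 + 0.84)/√n. This gives 0.23 SD at n = 150 and 0.40 SD at n = 50.
- Observed mean that reaches p < 0.05 = 1.96/√n. This gives 0.16 SD at n = 150 and 0.28 SD at n = 50.
- False-positive rate = Φ(b√n − 1.96) + Φ(−b√n − 1.96).

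For b = 0.1 and n = 150, b√n = 1.225, so the rate is Φ(−0.735) + Φ(−3.185) = 23.2%.

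| Shift b (SD) | n = 50 | n = 150 |
|---|---|---|
| 0 | 5.0% | 5.0% |
| 0.05 | 6.4% | 9.4% |
| 0.1 | 10.9% | 23.2% |
| 0.2 | 29.3% | 68.8% |
| 0.3 | 56.4% | 95.7% |

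For any non-zero shift the rate is higher at the larger n, so sample size gives no protection. The table does not show which row applies.

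**The case against.** The case on the other side has five parts.

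- **Knowledge of the day is inferred.** A reader might infer that the site researchers know which day they are reading. The protocol does not say so. The None in the synopsis may refer only to treatment allocation, and recording findings after each test need not be the moment when thresholds are adjudicated. This stands: the supportable statement is that no masking is provided.
- **The contrast is not named.** A reader might infer that the day-1 versus day-2 change in VT1 is the study's main comparison. The aims and Section 4.5 do not say that, and coming first in a list is not a ranking. Section 4.1.6 gives VO2 peak as the leading reason for CPET, and neither VO2 peak nor end-tidal CO2 needs a threshold reader. This also stands.
- **There are safeguards.** The nadir checks are tied to minima in the recorded data and limit how far a threshold can be moved, and adjudication settles disagreement. They narrow the room for bias. They do not close it, because the adjudicator is unmasked too.
- **The detail may sit elsewhere.** File coding and reading order are often set in an analysis plan or a reading procedure, and nothing in Section 4.1.6.1 forbids masked reading. That is fair, but this protocol chose to specify who reads and how disputes are resolved. The procedure it fixed is weaker than one available with the same staff.
- **The size cannot be derived.** It is tempting to convert the concern into physical units. One 30-second step (half a minute) in opposite directions on the two days, at 5 W per minute, gives 2 × 0.5 × 5 = 5 W. At 10 ml/min per W that is 50 ml/min, or 5% to 7% of a VT1 of 1000 to 700 ml/min. The documents do not support this as an estimate. Section 4.1.6 gives 5 W increments but no stage duration, and the oxygen cost and VT1 values are assumed. The scenario also needs an agreed shift across participants, for which there is no evidence. Even the 30-second unit is uncertain, since Section 4.1.6 mentions 30-second averages and Section 4.1.6.1 a smoothed breath-by-breath trace.

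**Conclusion.** The concern holds in a limited form. The protocol fixes a judgement-based reading of two key variables by site researchers and provides no masking to test day for them or for the adjudicator. Any day-1 versus day-2 threshold comparison is therefore open to day-related expectation.

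The size of any bias is unknown. The false-positive rates above show sensitivity under assumed shifts and do not estimate what will happen here. The conclusion rests on two inferences: that a day comparison of thresholds will be made, and that readers will usually be aware of the day. Both are reasonable from the design, and neither is stated. The point does not extend to VO2 peak or end-tidal CO2, and it does not show that any reading will in fact be biased. The change should still be made, because it is inexpensive and the bias cannot be removed afterwards by analysis alone.

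**What to change.** In Section 4.1.6.1, specify that:

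- exported traces are given coded file names without date or test order, and are presented in random order;
- the existing two readers read independently, with test day, symptom data and the other day's reading hidden;
- the adjudicator is masked in the same way;
- where possible, the reader is not the person who ran that test, since site staff may occasionally recognise a trace;
- inter-reader agreement is reported for VT1 and RCP.

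In Section 4.0, allow VT1 and RCP to be entered after masked reading instead of at the end of each test.

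The cost is one file-coding step and a short delay before thresholds are available. Data are already exported for offline analysis and the readers are already in place, so the sample size and the conduct of the test are unchanged. Masking reduces day-related expectation bias. It does not reduce random reader error, which is why agreement should be reported alongside.

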## 4.2 Follow-up Assessments

Using a custom developed application alongside commercially available heart rate monitoring devices, participants will be asked to provide accelerometry (asked through the participants phone), heart rate variability (iHeart) and a subjective wellness score for each day following baseline and CPET investigations each for a period of 3 days. This custom developed software has been developed at the Advanced Wellbeing Research Centre to provide objective and subjective assessment of fatigue in people suffering with long covid and has successfully been piloted with over 200 individuals. Where smartphone data is not possible, individuals will be asked to wear an accelerometer and subjectively report their wellness through patient diary.

## 4.3 Safety of Graded Exercise Testing

Graded exercise testing is a safe procedure which is routinely used in clinical, exercise and research settings. Numerous studies that have assessed the safety of graded exercise testing (mostly in cardiac patients) indicate that the risk of exercise-induced complications and mortality is very low. The reported mortality rate ranges from 0 to 1 death per 10,000 tests, and the non-fatal adverse event rate ranges from 0 to 5.2 per 10,000 tests.

## 4.4 Risk Management

### 4.4.1 Cardiovascular Risk

Participation in aerobic exercise may increase the risk of cardiovascular complications such as cardiac ischaemia, arrhythmia or hypotension. The use of an appropriate graduated warm-up and cool-down is recommended to minimise these risks (ACSM, 2021). In the proposed study, participants' physiological response to exercise will be closely monitored during and after exercise. Exercise will be stopped if any adverse signs or symptoms occur (see table above). The researcher is experienced in the provision of clinical exercise tests and is trained in cardiopulmonary resuscitation.

### 4.4.2 Musculoskeletal Risk

Participation in aerobic exercise may increase the risk of musculoskeletal injury such as a muscle strain. This risk will be minimised by conducting a graduated warm-up and by following the cycle ergometer manufacturer guidelines regarding correct positioning of participants.

### 4.4.3 Post-Exertional Malaise

Post exertional malaise has been identified in patients with long covid especially with incremental exercise and exertion. We will screen for individuals' experiences PEM

prior to the study and follow up with individual participants following baseline measurement sessions before proceeding with repeated day CPET. Those individuals who show symptoms of PEM will be provided with guidance of pacing and provided with access to published materials around managing fatigue as per UK NHS long covid clinic guidance (World Physiotherapy, 2021).

#### **4.4.4. Bruising.**

Bruising may occur following venepuncture sampling, participants will be advised of this through PIS and management if bruising occurs (Rest and cold exposure).

### **4.5 Statistical Analysis**

Statistical analysis will be supervised by [name] at the University of Derby and conducted using SPSS version 26. This study is a prospective observational cohort study, designed to identify suitable tools and measures across different domains for assessing patient recovery from COVID-19.

Descriptive statistics will be calculated for all outcomes of interest. These will be presented as proportions and means with standard deviations or medians with interquartile ranges, depending on the distribution of data.

Within group differences will be compared using parametric (students t-test) and non-parametric (Mann-Whitney U, Chi square) tests, depending on normality of distribution.

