### 2.2 Secondary Aims

- Examine the relationship between COVID-19 symptom prevalence and exercise tolerance
- Examine the prevalence of post-exertional malaise in people with long covid.
- Examine the role of vaccination history (COVID-19) on exercise tolerance.

- Assess cardio-respiratory responses to physiological stress and provide insight regarding the integrity of the pulmonary-vascular interface and characterization of any impairment or abnormal cardio-respiratory function.

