## 3.0 Study Design

A multicentre, cross-sectional, observational study.

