#### 4.1 Baseline Clinical Data

Data collected will include demographics, the pre-admission symptoms, pre-admission therapy, preadmission exercise tolerance and performance status (retrospective assessment by the patient and/or representative 6 weeks preceding admission) level of educational attainment, past-medical history, time and route of admission, and in-hospital routine physiological observations (including heart rate, blood pressure, oxygen saturation, respiratory rate and temperature). Blood biomarkers that are part of clinical profiling such as CRP, total blood count, D-Dimers and IL-6 as well as exploratory markers for Long covid mechanisms including inflammatory responses and clotting factors. This will also be performed pre and post (30mins) exercise bouts..

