##### 4.1.2 Questionnaires

###### 4.1.2.1 Symptom Profile

Symptom profile will be measured twice at the baseline assessment (Day 0), to capture a) retrospective assessment by the patient of their symptom status at symptom onset (essentially their baseline symptoms), and b) their current symptom status at the point of testing.

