#### **4.1.2.6 Post-COVID-19 Functional Status (PCFS) Scale**

The Post-COVID-19 Functional Status (PCFS) Scale will be assessed upon discharge from the hospital and during each face-to-face visit to monitor direct recovery and to assess functional sequelae. The PCFS will evaluate the ultimate consequences of COVID-19 on functional status and supplement other instruments that measure quality of life, tiredness, or dyspnoea in the acute phase. The PCFS covers the full spectrum of functional outcomes and focuses on both limitations in usual duties/activities and changes in lifestyle in six scale grades. Briefly grade 0 reflects the absence of any functional limitation, and the death of a patient is recorded in grade D. Upward of grade 1, symptoms, pain or anxiety are present to an increasing degree. This has no effect on activities for patients in grade 1, whereas a lower intensity of the activities is required for those in grade 2. Grade 3 accounts for inability to perform certain activities forcing patients to structurally modify these. Finally, grade 4 is reserved for those patients with severe functional limitations requiring assistance with activities of daily living (ADL).

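### Section 4.5 assigns the Mann-Whitney U and chi-square tests, which compare different people, to within-group differences in one cohort measured repeatedly

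*Protocol*

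**What the plan says.** Section 4.5 follows its description of summary statistics with one sentence on testing: "Within group differences will be compared using parametric (students t-test) and non-parametric (Mann-Whitney U, Chi square) tests, depending on normality of distribution". The section names no paired or repeated-measures procedure, unless the t-test is meant in its paired form.

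There is one cohort of 150 and no comparator arm. The same people are measured repeatedly:

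- **Accelerometry (section 4.0):** "Patients will wear accelerometers during this period to compare baseline and follow up". This is the one within-person contrast that the protocol states outright.
- **PCFS, an ordinal scale (section 4.1.2.6):** it "will be assessed upon discharge from the hospital and during each face-to-face visit to monitor direct recovery".
- **Exercise testing (synopsis, description of interventions):** "Consecutive day 2 day CPET and follow up for 7 days for subjective feelings/fatigue".
- **Blood markers (section 4.1):** "This will also be performed pre and post (30mins) exercise bouts".
- **Symptom profile (section 4.1.2.1):** recorded twice on Day 0, once recalled for symptom onset and once for the current state.

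Other parts point to comparisons between people. Section 2.2 has the aim "Examine the role of vaccination history (COVID-19) on exercise tolerance", section 4.0 stratifies by demographic and physiological variables, and section 3.0 calls the design "A multicentre, cross-sectional, observational study". Section 4.5, by contrast, calls it a prospective cohort intended to find measures of recovery.

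**The concern.** Mann-Whitney U and the chi-square test of independence treat the two sets of values as coming from different people. When each person supplies both values, the variance between people cancels from the change, but these tests leave it in the error term. With positive within-person correlation they become conservative: they reject far less often than 5% under no change and miss small real changes.

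Chi-square can also go wrong in another way. Run on the cross-table of first against second measurement, it tests whether the two are associated, not whether anything changed.

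The study sets out to describe recovery and the response to exertion, so small within-person changes are part of what it may need to see. The protocol states no hypothesis about day 1 against day 2. The point therefore applies to whichever within-person contrasts are tested.

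**Working it through.** **Inputs.** From the protocol: n = 150 (50 per centre) and the tests named in section 4.5. It gives no alpha, SD, effect size or within-person correlation for these comparisons, so there is no planned figure to reproduce. Assumed: two-sided 5%, correlation r from 0.5 to 0.95, shifts of 0.2 to 0.4 SD.

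**Standard error of a mean change.**

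- Independent-samples formula: SD × √(2/n)
- True value for paired data: SD × √(2(1 − r)/n)
- Ratio: 1/√(1 − r) = 1.41, 1.83, 3.16 and 4.47 at r = 0.5, 0.7, 0.9 and 0.95

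**Normal approximation at r = 0.7, shift 0.2 SD, n = 150.** The standardised shift is 0.2 × √(150/2) = 1.732, and √(1 − 0.7) = 0.548.

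- Unpaired test: 1 − Φ((1.960 − 1.732)/0.548) = 1 − Φ(0.416) ≈ 0.34
- Paired test: Φ(1.732/0.548 − 1.960) = Φ(1.202) ≈ 0.885
- True type I error of the unpaired test: 2 × (1 − Φ(1.960/0.548)) ≈ 0.0003

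**Simulated power, n = 150, 5,000 replicates per cell (Mann-Whitney / signed-rank).**

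| Data and shift | r = 0.5 | r = 0.7 | r = 0.9 | r = 0.95 |
|---|---|---|---|---|
| Normal, 0.2 SD | 0.359 / 0.662 | 0.322 / 0.870 | 0.222 / 1.000 | 0.179 / 1.000 |
| Normal, 0.3 SD | 0.784 / 0.943 | 0.845 / 0.997 | 0.954 / 1.000 | 0.990 / 1.000 |
| Normal, 0.4 SD | 0.973 / 0.998 | 0.993 / 1.000 | 1.000 / 1.000 | 1.000 / 1.000 |
| Lognormal, 0.2 | 0.348 / 0.623 | 0.311 / 0.826 | 0.240 / 0.999 | 0.179 / 1.000 |
| Lognormal, 0.4 | 0.972 / 0.994 | 0.994 / 1.000 | 1.000 / 1.000 | 1.000 / 1.000 |
| Ordinal, 0.2 SD | 0.307 / 0.560 | 0.285 / 0.751 | 0.211 / 0.973 | 0.171 / 0.997 |
| Ordinal, 0.4 SD | 0.952 / 0.992 | 0.976 / 0.999 | 0.998 / 1.000 | 0.999 / 1.000 |

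The lognormal data have a log-SD of 0.6, with the shift in log-SD units. The ordinal data have four grades with assumed shares of 30, 35, 25 and 10%; shift and correlation are on the latent scale.

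With no change, Mann-Whitney rejects in 0.007 to 0.010 of samples at r = 0.5 and in at most 0.001 at r ≥ 0.7. Signed-rank rejects in 0.045 to 0.053. A second simulation with normal data and 4,000 replicates agrees: 0.30 against 0.86 at r = 0.7, 0.2 SD, n = 150. For one centre (n = 50) at r = 0.8 it gives 0.03 against 0.57.

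**Binary illustration.** Suppose 90 of 150 people have a feature first and 105 of 150 later. Chi-square on the two totals:

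- Pooled proportion 195/300 = 0.65
- z = 0.10/√(0.65 × 0.35 × 2/150) = 0.10/0.0551 = 1.816
- χ² = 3.30, p = 0.069, whatever the pairing

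Exact McNemar for three pairings with the same totals:

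| Gained / lost | phi | p |
|---|---|---|
| 16 / 1 | 0.77 | 0.0003 |
| 20 / 5 | 0.65 | 0.004 |
| 25 / 10 | 0.51 | 0.017 |

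**Chi-square on the cross-table.** Take 80 yes-yes, 10 yes-no, 10 no-yes and 50 no-no, so there is no net change. Then χ² = 150 × (80 × 50 − 10 × 10)²/(90 × 60 × 90 × 60) = 78.2, p < 0.001, while McNemar gives p = 1.0.

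**The case against.** **The subgroup reading.** The phrase may mean comparisons between subgroups inside the one cohort. The vaccination aim, the stratification in section 4.0 and the cross-sectional label in section 3.0 support this, and the named tests would then be valid. This stands as a possible reading, but it does not rescue the sentence: *within group* is the wrong term for it, and the only inferential statement would then cover none of the repeated data.

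**Left to the analysis plan.** The choice of test for repeated measures could be left to an analysis plan. That would answer a complaint about missing detail. Here the protocol names specific tests and attaches them to a comparison that, read in the ordinary way, they do not suit.

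**Loose naming.** Student's t-test can be the paired form, and it is not criticised. Chi-square might loosely include McNemar, whose statistic is referred to a chi-square distribution. McNemar is ordinarily named separately, however, and Mann-Whitney has no paired form.

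**Few stated contrasts, assumed size.** Only accelerometry is explicitly to be compared over time, and the t-test may cover it. The cross-table case is hypothetical, since no binary day-1/day-2 endpoint is stated. Correlation, effect size and discordant counts are all assumed. The four-grade ordinal case follows the synopsis; section 3.3 also excludes PCFS grade 1, which would leave three grades. These limits stand. They bear on the size of the loss, not on the mismatch.

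**Conclusion.** The concern holds. Read in the ordinary way, section 4.5 prescribes independent-samples tests for paired data. Read as subgroup comparisons, it mislabels them and covers none of the repeated measurements. The sentence needs correcting on either reading.

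The error is conservative, so it does not threaten false positives, except where chi-square on a cross-table is mistaken for a test of change. The loss is large for small changes: at 0.2 SD, normal data and n = 150, power is 0.36 to 0.18 for Mann-Whitney against 0.66 to 1.00 for signed-rank over r = 0.5 to 0.95. It shrinks at 0.3 SD (0.78 to 0.99 against 0.94 to 1.00) and is small at 0.4 SD. These figures rest on assumed correlations and shifts. The mismatch itself rests only on the protocol's wording and its visit schedule.

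**What to change.** Replace the sentence in section 4.5 with two:

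> Within-participant comparisons between two time points will use the paired t-test or the Wilcoxon signed-rank test (continuous or ordinal outcomes, according to the distribution of the paired differences) and McNemar's test (binary outcomes). The independent-samples t-test, Mann-Whitney U and chi-square tests will be used only for comparisons between different participants, for example by vaccination history.

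This also stops the choice of chi-square from appearing to depend on normality; it depends on the outcome being categorical. Outcomes recorded at more than two visits, such as the PCFS, need a method for more than two time points, for example a mixed model with participant as a random effect. That can be set out in the analysis plan.

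The cost is two sentences, changed before the analysis. No new data, visits or participants are needed.
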